#### 8.6.4. Medication Effectiveness

Among patients with at least one year of follow up, medication effectiveness at one year after the index date will be determined using the following six criteria. For each of the 6 criteria, a 0/1 flag will be created. Patients who are effectively treated for each of the 6 criteria will be considered effectively treated. Patients who fail any of the 6 criteria are therefore not effectively treated.

1. High adherence to index agent: a proportion of days covered (PDC) will be calculated based on total days supply over the 1 year follow-up. The PDC will be calculated by using the date of service and the day supply for each fill of the index medication. For patients that receive both 5mg and 11mg tofacitinb, both configurations will be treated interchangeably. Patients with early refills will be allowed to stockpile medications up to a maximum of 14 days total for later use.

---

 Curtis, J.R., et al., *Derivation and preliminary validation of an administrative claims-based algorithm for the effectiveness of medications for rheumatoid arthritis*. *Arthritis Res Ther*, 2011. **13**(5): p. R155.

 Oladapo, et. al. *Medication Effectiveness with the Use of Tumor Necrosis Factor Inhibitors Among Texas Medicaid Patients Diagnosed with Rheumatoid Arthritis*. *Journal of Managed Care Pharmacy*. 657 – 67. Vol. 20, No. 7. July 2014

2. No increase in dose for index medication compared to the starting dose. Dose escalation will be identified per the criteria listed in [Table 2](#).
3. No switching from the index medication to a (different) biologic agent or tofacitinib. A switch will be defined as use of a different biologic or tofacitinib any time during the follow-up period.
4. No adding of a new non-biologic DMARD to the index therapy. Adding a new non-biologic will be considered as having at least 1 claim for one of the 3 main:
  1. NB-DMARDs during follow-up and not having a claim for the same NB-DMARD during the baseline. Changing from 1 NB-DMARD at baseline to a different.
  2. NB-DMARD at follow-up will be considered as adding a new NB-DMARD, ie, failing the algorithm.
5. Oral glucocorticoids. Only National Drug Code (NDC) codes for oral glucocorticoids will be included:
  - a. For patients with no claims for oral glucocorticoid prescriptions in the six months prior to the index date: cannot receive more than 30 days of oral glucocorticoids between (index date +91) to (index date + 359). 30 days of oral glucocorticoids will be determined by summing up the day supply of all glucocorticoids claims with a fill date between (index date +91) to (index date +359).
  - b. For patients with claims for oral glucocorticoids during the six months prior to the index date: No increase in oral glucocorticoid dose during months 6-12 after:
    - a. Index compared to the 6 months before the index date. Increase in oral glucocorticoids will be determined from the prednisone equivalent dose for all glucocorticoid claims filled during the respective time periods.
6. At most one parenteral or intra-articular glucocorticoid joint injection on unique days after the patient had been on biologic treatment for more than three months between (index date +91) to (index date +359).

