### 8.2.1. Inclusion Criteria

This study will include individuals who are privately insured and with Medicare Supplemental insurance paid for by their employers and initiating tofacitinib in combination with MTX for RA between 01 January 2014 and 31 January 2017. To be included in the final study sample, patients must meet the following inclusion criteria:

1. At least one claim for tofacitinib between 01 January 2014 and 31 January 2017 (the identification period).

- a. **Medication index date.** The index date will be the date of the first claim for tofacitinib during the identification period.

*Note: Patients will have a variable length baseline of at least a year long. The baseline period will be censored at January 1, 2012 based on licensed data availability. The majority of baseline measures will use data from the 12 months immediately prior to the index date. Select measures will use data during the entire variable length baseline.*

- b. Tofacitinib initiation. Patients must have a 2nd claim for tofacitinib within 60 days of the end of the days supplied from their index claim (at least two claims with no 60 day gap).
- c. Oral MTX initiation. Patients must have an initial prescription for oral MTX in the period between 30 days prior to index date and 30 days following index date followed by a 2nd prescription for oral MTX within 60 days of the end of the days supplied from their initial MTX claim (at least two claims/administrations with no 60 day gap).

2. Presence of The International Classification of Diseases, 9th Revision, Clinical Modification (ICD-9 CM) code for RA (in any position) during the one-year pre-index period or on the index date. ICD-9 = 714.0x-714.4x & 714.81 or ICD10 = M05.\* & M06.0\*-M06.3\* or M06.8\*-M06.9\*.

3. At least 18 years old as of the index date.

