### 8.5. Period of Observation

All patients will be required to be continuously enrolled in the health plan for at least 24 months. Patients will have a variable length baseline period of at least 12 months. The 12 months prior to the index date will be used to assess the majority of pre-index characteristics. However, for select measures, eg, number of prior biologic therapies, and years since first RA diagnosis, the entire variable length baseline period will be utilized.

Measures utilizing the variable length baseline are noted. All baseline periods will be censored at January 1, 2012. The twelve months following the index date will be used to assess outcomes including treatment patterns, and health care costs, utilization and medication effectiveness.

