### 8.6.5. Health Care Cost and Utilization

All cost and utilization measures will be identified in the 12-month pre-index period and the 12-month post-index period. Claims occurring on the index date will be considered part of the post-index period. Baseline and follow-up costs and the change in 12-month costs from baseline to follow-up will then be examined. Cost measures will comprise the total amount paid by the health plan and patient.

- **Health care resource utilization**-Health care resource utilization will be calculated for ambulatory visits (office and outpatient), emergency department (ED) visits, and inpatient admissions.
- **RA-related resource health care utilization**-Health care resource utilization related to RA will be calculated for ambulatory visits, emergency room (ER) visits, and inpatient admissions. Utilization will be defined as RA-related if the claim had a diagnosis for RA in any position and/or is for the administration of a biologic or NB-DMARD.
- **Health care costs**-Health care costs will be computed as the combined health plan and patient paid amounts. Costs will be calculated as total costs, pharmacy costs, and medical costs. Medical costs will be further broken down into ambulatory costs, emergency services costs, inpatient costs, and other costs. Costs will be adjusted using the annual medical care component of the Consumer Price Index (CPI) to reflect inflation between 2013 (the earliest start of the pre-index period) and 2015 (the cost of claims occurring in 2016 will not be adjusted).

Costs from other payers are of importance for older patients dually eligible for commercial and Medicare coverage. Payments from Medicare (and other payers) will be estimated based on coordination of benefits information obtained by the health plan in its usual course of business. This study will incorporate the amounts estimated to be paid by other payers for a total paid or allowable amount.

[figure not shown]

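### Effectiveness criterion 3 (section 8.6.4) names tofacitinib, the index drug for every patient, as a switch, so a literal coding leaves no patient effectively treated

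*Combined protocol and SAP*

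**What the plan says.** Section 8.2.1 makes tofacitinib the only index drug: "The index date will be the date of the first claim for tofacitinib during the identification period". Criterion 1b of the same section then requires a second "claim for tofacitinib within 60 days of the end of the days supplied from their index claim". Section 8.5 sets the outcome window: "The twelve months following the index date will be used to assess outcomes".

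Section 8.6.4 defines effective treatment by six criteria, all of which must be met: "Patients who fail any of the 6 criteria are therefore not effectively treated". Criterion 1 asks for high adherence to the index drug. Criterion 3 has two sentences. The first states the requirement, "No switching from the index medication to a (different) biologic agent or tofacitinib", and the second gives the working definition, "A switch will be defined as use of a different biologic or tofacitinib any time during the follow-up period".

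Section 8.6.3 also describes switching, as a treatment pattern. There the switch target is always a biologic other than the index drug. Section 8.6.4 does not refer back to that wording.

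**The concern.** The second sentence of criterion 3 is the one a programmer would code, and it lists tofacitinib without qualification among the drugs whose use in follow-up is a switch. In a study with several index drugs, such wording could make sense for patients who started on something else. Here everyone started on tofacitinib, so remaining on the study drug satisfies the definition of leaving it.

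Medication effectiveness is the third secondary objective in section 7. Under section 8.10 its descriptive result is the percentage effectively treated at one year, and its possible multivariable analysis is a logistic regression of that yes/no outcome. If the outcome takes one value for everyone, neither can compare the cohorts.

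**Working it through.** The plan gives no figure to reproduce, so the check is one of logic with a little date arithmetic.

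**Step 1. Does every eligible patient have tofacitinib use in follow-up?** Inputs:
- The index date is day 0 (section 8.2.1, criterion 1a).
- The second claim comes no later than 60 days after the index supply ends (criterion 1b).
- The supply runs out on the service date plus days supplied minus 1 (the run-out rule in section 8.6.3).
- Follow-up is 12 months, taken here as days 0 to 364.
- The length of the index supply is not stated. I assume 30 to 90 days and also find the limit.

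Latest day of the second claim = days supplied − 1 + 60.

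| Index supply (days) | Latest day of second claim | Within day 364? |
|---|---|---|
| 30 | 30 − 1 + 60 = 89 | yes |
| 60 | 60 − 1 + 60 = 119 | yes |
| 90 | 90 − 1 + 60 = 149 | yes |
| 305 | 305 − 1 + 60 = 364 | yes (limit) |

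For any index supply up to 305 days, the required second claim lies inside follow-up. This holds whether or not the index claim itself is counted.

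**Step 2. Apply criterion 3 under two readings.**

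| Patient's claims in follow-up | Literal: a different biologic, or tofacitinib | Index drug excluded, as in 8.6.3 |
|---|---|---|
| Tofacitinib only | fails | passes |
| Tofacitinib, then a biologic | fails | fails |

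Under the literal reading the criterion does not separate the two patients. With the index drug excluded, it does.

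**Step 3. Carry this to the composite.** Let *p* be the proportion meeting the other five criteria. Under the literal reading the proportion effectively treated is *p* × 0 = 0 for any *p*. Assumed values of *p* of 0.2, 0.4, 0.6 and 0.8 all give 0. This holds in the discontinued, interrupted and persistent cohorts alike. With no events in any cohort, a logistic model has nothing to fit and the odds ratios cannot be estimated.

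**Step 4. Compare with criterion 1.** Criterion 1 can be met only by taking tofacitinib through the year. Literal criterion 3 can be met only by having no tofacitinib use in follow-up. The two are mutually exclusive.

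**The case against.** The best defence is that nobody would read criterion 3 this way. Its first sentence concerns moving away from the index drug, and a patient cannot move from tofacitinib to tofacitinib. The word *different* can be read as governing both nouns, in which case staying on the index drug never triggers the criterion. Section 8.6.3 points the same way, and the clash with criterion 1 itself shows that the literal result was not meant. A table showing 0% everywhere would be noticed. Section 8.11 has final deliverables verified by a second programmer, and section 8.12.1 foresees physician consultation on whether the algorithm needs modification.

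Most of this stands as evidence of intent. It does not repair the text. Section 8.6.4 carries its own definition without a cross-reference. Section 8.11 says the analyses are programmed from the protocol and, if applicable, a statistical analysis plan, and Annex 1 lists no stand-alone document that could override the wording. Annex 2 places tofacitinib in the same code list as the biologics, so a switch flag built from that list could include it. Reading *different* across both nouns also leaves a different tofacitinib with no clear meaning in a study with one index drug.

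Three further inferences are tempting, and the documents do not support them:

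- **That section 8.6.3 has the same error.** Its discontinue-then-switch category mentions tofacitinib in brackets, but it also requires the drug to differ from the index medication. Nobody is misclassified.
- **That counting a move between 5 mg and 11 mg as a switch would contradict the plan.** The sentence treating the two as interchangeable sits in criterion 1 and concerns the proportion of days covered. No section calls such a move a switch, and none rules it out under criterion 3. This is a gap to close, not a contradiction.
- **That the index-date rule proves the point.** The statement "Claims occurring on the index date will be considered part of the post-index period" is in section 8.6.5, for cost and utilization measures. Step 1 does not need it.

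**Conclusion.** The working definition in criterion 3 is wrong as worded. Applied literally, 100% of patients fail it, 0% are effectively treated in every cohort, and the effectiveness comparison cannot be estimated. This rests on tofacitinib being the only index drug, on the required second claim, and on an index supply of no more than 305 days.

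A reader might infer that the study will report 0% effectiveness. The documents do not support that: the intended meaning is recoverable, and the error would probably be seen at the first descriptive table. What is certain is narrower. A secondary endpoint has a stated rule that gives a useless result if followed, and sections 8.6.3 and 8.6.4 describe a switch differently with nothing to say which governs. The effectiveness rate under the corrected rule cannot be given, because the plan states no pass rates for the criteria. That the wording was carried over from a multi-drug protocol is plausible, since section 8.12.1 speaks of all biologic users, but the documents do not say so.

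**What to change.** In section 8.6.4, criterion 3:

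1. Delete the words *or tofacitinib* from both sentences.
2. Define a switch as use, at any time in follow-up, of any biologic other than the index medication (tofacitinib), in line with section 8.6.3.
3. State that a change between the 5 mg and 11 mg configurations is not counted as a switch for this endpoint.

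Removing the bracketed mention of tofacitinib from the discontinue-then-switch category in section 8.6.3 is optional tidying.

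The cost is a few words, made before the endpoint is programmed. It needs no new data and no change to the cohorts or the other five criteria.

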### 8.3. Cohort Assignment

Patients will be assigned to a study cohort based on MTX status following initiation of combination therapy with tofacitinib and MTX. The “MTX discontinued” cohort will contain patients who experience a gap in MTX therapy of >60 days within 12 months post-index. The “MTX interrupted” cohort will contain patients who experience a gap in MTX therapy of >60 days with 1 or more subsequent fills within 12 months post-index. The “MTX persistent” cohort will contain patients with no gap >60 days within 12 months post-index. If sample size is insufficient, the MTX “discontinued” and “MTX interrupted” cohorts may be combined.

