#### 8.6.2. Clinical Characteristics

- **Pre-index biologic use-**The use of biologics during the pre-index period will be identified. In addition, indicator variables will identify the specific biologic(s) used during the pre-index period. A count will be created to identify the number of different biologics received during the baseline. These measures will be created during the 12 month baseline and during the entire variable length baseline period.

- **Pre-index NB-DMARD use:** The use of the 4 main NB-DMARDs (methotrexate, sulfasalazine, hydroxychloroquine, and leflunomide), and the other NB-DMARDs will be identified during the pre-index period. In addition, indicator variables will identify the specific medications used during the pre-index period. A count will be created to identify the number of different NB-DMARDs received during the baseline. These measures will be created during the 12 month baseline and during the entire variable length baseline period.
- **Pre-index Quan-Charlson comorbidity score-**A comorbidity score will be calculated based on the presence of diagnosis codes on medical claims in the 12-months pre-index period. The Quan-Charlson comorbidity score will also be categorized into the following groups: zero, one to two, three to four, and five or more.
- **Comorbid conditions**—General comorbid conditions will be defined using the Clinical Classifications Software managed by the Agency for Healthcare Research and Quality (AHRQ). This measure generates indicator variables for specific disease conditions based on ICD-9-CM diagnoses. The top 25 comorbid conditions identified during the pre- and post-index period will be presented.
- **Pre-index claims based index of RA severity (CIRAS):** The claims-based index for RA severity will be implemented. CIRAS provides a single value of severity using the following 9 measures.

---

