  - **Discontinue without switch or restart.** Patients will be classified as discontinuing without switch or restart if they have a gap in therapy of at least 60 days and there are no claims for either the index med or a different biologic for the remainder of the follow-up period.
- **Switch any time.** In addition to the 4 mutually exclusive treatment patterns, patients with a switch medication any time during the 12-month follow-up period will be identified.

- **Restart any time.** In addition to the 4 mutually exclusive treatment patterns, patients who have a claim for the index medication any time after they are considered non-persistent with the index treatment (ie, including after switching) during the 12-month follow-up, will be identified.
- **Medication Possession Ratio (MPR):** In addition to the adherence measure in the medication effectiveness assessment (see [Section 8.6.4](#)), the MPR will be evaluated for persistent patients as the total days supply between the first and including the last prescription/administration divided by the time between the first through and including last biologic prescription/administration days supply. Adherent patients will be considered those with  $MPR \geq 0.8$ . For MPR calculations, multiple prescriptions having same fill date will be treated as one prescription with longest days supply; and for all prescriptions days supply will be capped at end of follow-up. Also, the MPR will be capped at 1.0.
- **NB-DMARD adherence/addition.** Adherence with MTX and addition of a non-biologic DMARD other than MTX (sulfasalazine, hydroxychloroquine, leflunomide) during the 12 month follow-up will be identified.
  - **MTX adherence.** A single measure of adherence (PDC) will be created using all claims for MTX during the 12-month follow-up period. Adherence will be calculated as the total day supply divided by the number of days from the first claim during the follow-up until the end of the follow-up.
  - **NB-DMARD addition.** Addition of a NB-DMARD will be evaluated.

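### Criterion 4 of the effectiveness outcome fails patients who replace MTX with another NB-DMARD, a route essentially closed to the MTX-persistent cohort, so the cohort comparison can be distorted in either direction

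*Combined protocol and SAP*

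**What the plan says.** Section 8.6.4 builds a yes/no outcome from six flags: "Patients who fail any of the 6 criteria are therefore not effectively treated".

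The text of criterion 4 is broken across list items, but its two parts can be read together. The first fails a patient with at least one follow-up claim for one of three main NB-DMARDs that was not claimed at baseline. The second covers a change of drug: "NB-DMARDs during follow-up and not having a claim for the same NB-DMARD during the baseline. Changing from 1 NB-DMARD at baseline to a different", continued in the next item as "NB-DMARD at follow-up will be considered as adding a new NB-DMARD, ie, failing the algorithm".

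The criterion does not name the three drugs. Section 8.6.2 lists four main NB-DMARDs, MTX among them: "The use of the 4 main NB-DMARDs (methotrexate, sulfasalazine, hydroxychloroquine, and leflunomide". Section 8.6.3 points to the other three, since it tracks "addition of a non-biologic DMARD other than MTX (sulfasalazine, hydroxychloroquine, leflunomide) during the 12 month follow-up will be identified".

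Section 8.3 sets the exposure. The discontinued "cohort will contain patients who experience a gap in MTX therapy of >60 days within 12 months post-index"; the interrupted cohort has such a gap with later fills; the persistent "cohort will contain patients with no gap >60 days within 12 months post-index". Section 8.5 measures outcomes over the same 12 months after index. Section 8.10 compares effectiveness across these cohorts, descriptively and possibly by logistic regression.

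**The concern.** The same sequence of claims can determine both cohort and outcome. If a patient stops MTX and starts leflunomide for the first time, the MTX gap puts that patient in the discontinued or interrupted cohort, and the leflunomide claim fails criterion 4. The number of NB-DMARDs has not risen. In the persistent cohort, failure on criterion 4 means a drug added to continuing MTX. One flag thus records replacement or add-on in one group and, in practice, only add-on in the other.

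A cohort difference in effectiveness could then reflect how often MTX was replaced as well as how patients fared on tofacitinib. The planned adjustment would not separate the two. The candidate covariates in Section 8.10.2 are mainly the patient and baseline clinical characteristics of Sections 8.6.1 and 8.6.2, and adjusting for them does not change what counts as failure. The decomposition in Section 8.10.6 would assign any part unrelated to those characteristics to treatment. Section 8.12.1 foresees physician consultation on the algorithm because it predates tofacitinib's approval, but does not mention this overlap.

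**Working it through.** The documents give no effectiveness rate, replacement rate, add-on rate or sample size calculation, so there is no planned figure to reproduce.

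**Step 1: trace the rules.**

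| Follow-up pattern | Cohort (8.3) | Criterion 4 (8.6.4) |
|---|---|---|
| MTX continued, nothing new | Persistent | Pass |
| MTX continued, new main NB-DMARD added | Persistent | Fail |
| MTX gap >60 days, nothing new | Discontinued or interrupted | Pass |
| MTX gap >60 days, main NB-DMARD already claimed at baseline | Discontinued or interrupted | Pass under the first part; the change rule leaves this unclear |
| MTX gap >60 days, new main NB-DMARD | Discontinued or interrupted | Fail |

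Replacement is essentially rather than strictly closed to persisters: a patient who stops MTX too late for a 60-day gap to complete within the 12 months stays in the persistent cohort.

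**Step 2: illustrate the size.** All inputs are assumptions.

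- *p*: probability of passing the other five criteria, the same in both cohorts, set at 40%.
- *s*: share of those otherwise-successful patients failing criterion 4 among withdrawers (discontinued or interrupted).
- *a*: the same share among persisters.

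Observed rates are p(1 − s) and p(1 − a). The odds ratio is the odds of the first over the odds of the second.

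| s | a | Withdrawers | Persisters | Odds ratio |
|---|---|---|---|---|
| 10% | 0% | 36% | 40% | 0.84 |
| 10% | 5% | 36% | 38% | 0.92 |
| 10% | 10% | 36% | 36% | 1.00 |
| 5% | 10% | 38% | 36% | 1.09 |
| 20% | 0% | 32% | 40% | 0.71 |

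First row: (0.36/0.64) / (0.40/0.60) = 0.5625/0.6667 = 0.84. Second row: 0.5625 / (0.38/0.62) = 0.5625/0.6129 = 0.92. Fourth row: 0.6129/0.5625 = 1.09.

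**Step 3: vary the inputs.** With a = 0, p from 20% to 40% and s from 5% to 30%, the deficit in withdrawers runs from 1 point (20% to 19%, odds ratio 0.94) to 12 points (40% to 28%, odds ratio 0.58). These are the figures with no add-on among persisters; any add-on there shrinks or reverses them. If replacement is concentrated in patients who fail another criterion anyway, s is smaller and so is the effect.

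**The case against.** The strongest reply is that criterion 4 never looks at MTX status. It applies one rule to everyone, and exposure and failure are defined by claims for different drugs. That is correct. A reader might infer that withdrawing MTX itself fails the algorithm, but the rule does not say so. What remains is that the uniform rule captures different events in the two groups.

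A reader might also infer that the comparison is tilted against withdrawal. The documents do not support that: persisters fail by add-on, and the table shows the effect cancelling or reversing at plausible rates.

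Second, needing a replacement drug may be a genuine failure of the withdrawal strategy, and ignoring it could label as effectively treated some patients who needed more therapy. The argument is coherent. The documents neither make it nor rule it out, so the six-criterion version should stay.

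Third, Section 8.6.4 says "For each of the 6 criteria, a 0/1 flag will be created", Section 8.10.1 promises descriptive analysis of all study variables by cohort, and Section 8.6.3 evaluates NB-DMARD addition separately. Criterion-level failure rates by cohort should therefore appear, and it would be too strong to call a difference uninterpretable. But no section separates replacement from add-on or plans the outcome without criterion 4. Section 8.10.2 also selects outcomes for modelling after the descriptive results are seen, so a version not fixed beforehand would be a post hoc choice.

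Finally, one might argue that the published algorithm was never meant for this comparison. That rests on papers not supplied with the plan, and the point does not need it.

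**Conclusion.** The point holds in a limited form. The effectiveness outcome contains a failure route, replacement of MTX by a new main NB-DMARD, that is linked to the exposure and essentially unavailable to the persistent cohort. The comparison can be distorted as a result, and a difference that depends on criterion 4 would be ambiguous. Neither size nor direction can be fixed from the documents: at an assumed 40% effectiveness in both cohorts, the cases with criterion 4 failure in both groups at 5% or 10% range from an odds ratio of 0.92 to 1.09, and 0.84 or 0.71 needs 10% or 20% failure among withdrawers and none among persisters. The calculation takes failure on criterion 4 as independent of the other five criteria, and the three main drugs to be those named in Section 8.6.3. This concerns one criterion of six in a secondary objective whose regression is optional. It is a cheap improvement, not a flaw that invalidates the study.

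**What to change.** Before the descriptive results are reviewed, add the following to Section 8.6.4 and the effectiveness part of Section 8.10:

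1. Keep the six-criterion outcome as planned.
2. Pre-specify a sensitivity version that omits criterion 4 for every cohort alike, analysed in the same way. Do not exempt only substitutions made after MTX stops: the same new claim would then fail a persister and pass a withdrawer, making the outcome rule depend on exposure.
3. Tabulate criterion 4 failures by cohort, split by claim dates into replacement (new drug started after MTX supply has run out) and add-on (started while MTX is still supplied). Fix that convention in advance, including how overlapping supply is classed.
4. Describe any cohort difference that appears only with criterion 4 as dependent on that rule.
5. In the same edit, repair the broken list, name the three drugs, and state whether baseline means 12 months or the full variable-length period, since each affects who fails.

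The cost is one extra model, built from flags already planned, and one table from claim dates already in the data. The downside is that the five-criterion version departs from the published algorithm and ignores true add-on failures, which is why it belongs beside the six-criterion result rather than in its place.
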